8.1.2.1 Prevalence of Osteoporosis

In the study, prevalence of osteoporosis in community-dwelling postmenopausal women in China will be investigated as a secondary objective. Descriptive statistics will be made to statistically address this objective. Point estimates (percentage) and corresponding 95% CI (exact binomial and Wilson score) will be presented for each analysis category and will be adjusted by age distribution in China [53]. Prevalence rates will also be given by age group and geographic region. A case with osteoporosis is counted based on the definition in Section 4.

The prevalence of osteoporosis will be presented as overall and by different diagnostic criteria and will be listed separately to allow an evaluation on the frequency distribution of each individual diagnostic setting in the study population.

The analysis of osteoporosis prevalence is displayed in the Table 8.1.2.1.

Table 8.1.2.1 Statistical Analysis Approaches on the Prevalence of Osteoporosis

Osteoporosis	Rate*	Estimate**	Frequency ***
Overall	Crude/Age-Standardized	Point and 95% CI	Percent
By DXA BMD [^]	Crude/Age-Standardized	Point and 95% CI	Percent
By Fragility Fracture [△]	Crude/Age-Standardized	Point and 95% CI	Percent & Cumulative

* Prevalence rates will be sub-analyzed by age group (50 – 54, 55 – 59, 60 – 65, 65 – 69, 70 – 74, 75 – 79, and 80+; and by < 65 and ≥ 65) and/or geographic region (North, South, Southeast, Southwest, and Central);
 ** Based on exact binomial distribution 95% CI and Wilson Score 95% CI;
 *** Calculation of frequency is relative to overall percent (100%);
 ^ the subject with a T-score ≤ -2.5 as suggested by a DXA measurement
 △ The subject with DXA measurement with a proven non-pathological major fracture as reported by the medical history or as suggested by radiology.

8.1.2.2 Risk Factors for Radiographic Vertebral Fracture or Densitometric Osteoporosis

As secondary objectives, all possible factors including socioeconomic status, lifestyle and clinical parameters will be assessed to identify if they are the risk factors of a prevalent vertebral fracture or densitometric osteoporosis in Chinese postmenopausal women.

A two-step statistical modeling will be established to assess the potential risks against the response of analysis interest (dependent variable). Initially, a single logistic regression for bivariate analysis will be used to give a percentage tabulation presenting proportions of case (morphometric vertebral fracture or densitometric osteoporosis) versus control by each analysis parameter. An odds ratio and associated probability (P value) will be given to examine the statistical significance of this independent variable in the model. A P value of 0.25 or less will be the criterion [54] for an entry into a multivariate logistic model for all estimated variables. Also, all clinically relevant variables, regardless of a probability level, will be included in the final model at the discretion of the study team.

Finally, a multivariable logistic regression model will be constructed for both dependent variables. A stepwise backward method to eliminate non-significant variables will be performed until all remaining variables in the model have a P value less than 0.1. The goodness-of-the-fit will be evaluated by using deviance and likelihood ratio tests and Hosmer–Lemeshow test [55] to assess if there is any single important variable missing from the model.

In the bivariate and multivariate analysis, age, BMD, and BMI will be fitted as continuous variables. Geographic region grouping study sites will be fitted as a categorical variable. Due to potential collinearity of BMD to vertebral fracture, BMD will also be introduced as a dichotomous variable (osteoporosis vs. normal and osteopenia). BMI may vary among study sites in the study, odds ratio per unit BMI instead of per standard deviation to minimize the biases upward.

8.1.3 Exploratory Objective(s): Calculation of Epidemiological Measure(s) of Interest (e.g. hazard ratios, incidence rates, test/retest reliability)

The diagnostic accuracy of onsite vertebral imaging will be tabulated by a simple 2*2 contingency table against blinded adjudication. Sensitivity, specificity, positive predictive value (PPV), negative predictive value (NPV), and likelihood ratio will be given with a corresponding 95% CI. Kappa test for inter-observer agreement between onsite and blinded experienced radiologists will be calculated and presented. Logistic regression model will also be used to assess the probability of a subject with adjudicated vertebral fracture will have the vertebral fracture as diagnosed onsite. The area under the Receiver Operating Characteristic (ROC) curve will be given to evaluate the degree of discrimination for the probability of interested response. Effects of age, region, and/or other analysis variables will be adjusted in the model whenever statistically appropriate.

Assessment in the diagnostic role of vertebral imaging for the screening of osteoporosis will be explored by a simple binary diagnostic test. An osteoporosis diagnosis in the study will be deemed as 'true condition' whereas the blinded vertebral imaging outcome will be the diagnostic tool. Sensitivity, specificity, PPV, NPV, and likelihood ratio will be presented with a corresponding 95% CI. Similarly, logistic regression model will also be used to assess the probability of a subject with adjudicated vertebral fracture will have densitometric osteoporosis. The area under the ROC curve will be given to evaluate the degree of discrimination for the probability of interested response. Effects of age, region, and/or other analysis variables will be adjusted in the model whenever statistically appropriate.

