3.5 Stratification

The subjects will be sampled and stratified according to the following factors:

- 1) Age;

Seven (7) age groups: 50 - 54, 55 - 59, 60 - 64, 65 - 69, 70 - 74, 75 - 79, 80 or above;

- 2) Geographic region;

Five (5) regions in China: North, South, Southeast, Southwest, and Central

4 Variables and Epidemiological Measurements

All eligible participants will be included in the study to an endocrinologist, or other specialist, whenever appropriate, for the collection of all clinical and radiological information by 1 onsite study visit in a cross-sectional fashion. Spine radiograph and/or DXA may be separated from onsite interview by a follow-up visit as determined by the investigator.

Questionnaire

All demographic data, socioeconomic status, lifestyle information, and clinical features including medical history/concomitant medications, will be collected by an interviewer-administered questionnaire performed by the investigator. The questionnaire will be designed to adapt China's cultural and clinical practice. The analyzable variables derived from the questionnaire include (but not limited to):

- Age (absolute value and category);
- Place of birth and dwelling geographic region;
- BMI (height and weight, as measured in the site);
- Social status and lifestyle (educational level, occupation, monthly income, physical exercise, diet, smoking, alcohol intake, diet, calcium intake);
- Clinical features (age and years of menopause, medical history, history of osteoporosis and parental osteoporosis, any prior fractures, prior and concomitant medication, antiresorptive treatment, glucocorticoid treatment, other treatment reducing bone mass);
- FRAX score (as determined by self-reported fracture and radiology evidence and calculated based on the information from questionnaire with/without BMD).

BMD Measurement

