6.1.2 Clinical Procedures/Assessments

6.1.2.1 Questionnaire and Physical Examination

The study's questionnaire will be developed based on questionnaires of previous large studies [29-34] and is attached in the Section 11 Appendices. During the investigator's meeting and training session, the questionnaire will be reviewed and discussed in order to clarify terms, country features, and standardization. The investigator will have training in understanding the questionnaire before the study enrollment. The questionnaire will be delivered by Chinese simplified written language. In order to minimize variability, it is preferred that the same individual investigator (s) perform questionnaire interviews for all subjects at each study site.

The questionnaire will collect self-reported data on demographics, gynecological history, socioeconomic status, life style factors, and clinical risk factors for osteoporosis. Commercial calcium supplement and vitamin D intake will be calculated according to names and daily doses reported by participants. Alcohol intake will be calculated in grams per day and be categorized according to the WHO as: never, for the subject who does not report alcohol intake; mild, from 1 to 10 grams per day; moderate, from 11 to 40 grams per day; and severe, for more than 40 grams per day. For smoking history, information on time and average number of cigarettes (and any other type of tobacco) consumed will be obtained. Physical activity will be assessed in minutes per day according to time spent on various activities including walking, dancing, and other Chinese specific outdoor activities.

All other major risk factors will be based on self-reported during the interview administered by the investigator. The subject's symptoms/signs and medical records will be reviewed for possible medical history. Comorbidities including asthma, chronic obstructive pulmonary disease (COPD), and diabetes mellitus are defined in the study (Refer to 'List of Definitions') and all definitions of diseases will be provided and further explained by the investigator during the interview. A detailed history of any fracture (after age of 40, anatomical site and the level of trauma) and height loss will be collected; prior and concomitant medications regarding steroids use, hormone replacement therapy (HRT), and any use of antiresorptive drugs will be recorded for medication name, daily dose and treatment duration.

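### Section 8.1.2.2 selects risk factors by P value from every available variable, with no rule keeping out those that contain the outcome or follow from it

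*Combined protocol and SAP*

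**What the plan says.** Section 8.1.2.2 covers two of the three secondary objectives in section 2.2. It states that "all possible factors including socioeconomic status, lifestyle and clinical parameters will be assessed to identify if they are the risk factors" of the two outcomes. Each candidate first goes into a single-variable logistic regression: "An odds ratio and associated probability (P value) will be given to examine the statistical significance of this independent variable in the model". For entry to the multivariable model, "A P value of 0.25 or less will be the criterion". In addition, "all clinically relevant variables, regardless of a probability level, will be included in the final model at the discretion of the study team". Backward elimination then runs "until all remaining variables in the model have a P value less than 0.1". The section names age, BMD, BMI and region as covariates. It gives no candidate list and no rule on timing or on variables derived from the outcome.

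The pool of candidates has to be read from elsewhere. The questionnaire part of section 4 gives an open list of analysable variables. It includes history of osteoporosis, "any prior fractures, prior and concomitant medication, antiresorptive treatment" and a "FRAX score (as determined by self-reported fracture and radiology evidence", calculated with or without BMD. Section 6.1.2.1 adds that a detailed fracture history, with anatomical site, and "height loss will be collected".

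**The concern.** A risk factor should precede the outcome and be measured independently of it. Several variables in this pool fail one or both tests for prevalent vertebral fracture, and P-value selection cannot tell a cause from a consequence. A strong consequence passes as easily as a strong cause.

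At stake is the answer to the risk-factor objectives. It goes further than that, because section 3.1 says the analyses will be expanded into a vertebral fracture risk assessment model. A predictor that already contains the film reading would make such a model look better than it is. A drug started because of a fracture could appear to raise the risk of fracture.

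**Working it through.** **1. Size of the data set.** The age-group sizes in Table 8.3.1 sum to 518. Dividing by 1 − 0.05 gives 545.3, which matches the stated 545 per region. Five regions give 2,725, close to the stated 2,700. Multiplying each age-group size by its assumed prevalence gives 2.2 + 5.67 + 12 + 14.4 + 16 + 16.1 + 19.61 = 85.98 cases per region. That is 16.6% of 518, or about 430 cases over five regions. The plan states no figure for the risk-factor models themselves.

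**2. How each variable relates to vertebral fracture, on the documents' own account.**

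| Variable | Source | Relation to the outcome |
|---|---|---|
| FRAX | Section 4 | Fracture input uses self-report and radiology. The definition of osteoporosis in section 4 lets study imaging establish a fragility fracture, so the outcome may be an input |
| Height loss | Section 6.1.2.1 | Section 1.1 describes it as one way a vertebral fracture shows itself |
| Prior vertebral fracture | Sections 4 and 6.1.2.1 | May be the same deformity that the film shows |
| History of osteoporosis | Section 4 | May rest on an earlier fracture or BMD reading, since either meets the definition in section 4 |
| Antiresorptive use | Sections 4 and 6.1.2.1 | Section 1.1 treats a diagnosed vertebral fracture as a reason for drug therapy |

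**3. Do the selection rules screen these out?** An illustrative simulation used 300 runs per scenario, the prevalences of Table 8.3.1 and about 2,460 women (518 × 5 × 0.95, slightly below the 2,590 implied by 518 × 5). Each variable was generated after the fracture with no causal effect on it. It was kept if its bivariate P was at most 0.25 and its age-adjusted P was below 0.1. All effect sizes are assumptions.

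- FRAX: if film fracture multiplies the score by 1.5 or 2.0, it was kept in 100% of runs. With no film input it was kept in 11%, about what a 0.1 threshold gives by chance.
- Height loss (SD 2.5 cm): kept in 44%, 97% and 100% of runs if fracture adds 0.2, 0.5 and 1.0 cm.
- Antiresorptive use, with 25–33% of fractures diagnosed: kept in 99–100% of runs if 30–50% of diagnosed women and 5% of others are treated (median adjusted odds ratio 2.4 to 4.7). If the shares are 20% and 10%, it was kept in 44–61% (odds ratio 1.3 to 1.4).

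**4. Range of the odds ratio for antiresorptive use.** Let b be use among women without fracture, θ the true odds ratio, d the share of fractures diagnosed, and t the share of diagnosed, otherwise untreated women who start treatment. With o = b/(1 − b):

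- p0 = θo/(1 + θo)
- p1 = p0 + (1 − p0)·d·t
- observed odds ratio = [p1/(1 − p1)]/o

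Example: b = 5%, θ = 0.6, d = 25%, t = 30%. Then o = 0.0526, p0 = 0.0306, p1 = 0.0306 + 0.9694 × 0.075 = 0.1033, and the odds ratio is 0.1152/0.0526 = 2.2.

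| b | t | θ | Observed odds ratio, d from 25% to one third |
|---|---|---|---|
| 5% | 30–50% | 1.0 | 2.6–5.0 |
| 5% | 30–50% | 0.6 | 2.2–4.5 |
| 10% | 20% | 0.6 | 1.1–1.3 |
| 15% | 20% | 0.6 | 0.93–1.05 |
| 10% | 10% | 0.6 | 0.85–0.93 |

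Only d comes from the documents. Section 1.1 gives one fourth to one third for incident fractures, and applying it to prevalent ones is an assumption. The formula is unadjusted.

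**5. The densitometric-osteoporosis model.** Section 8.1.2.2 fits BMD in the bivariate and multivariate analyses without limiting it to the fracture outcome. The outcome here is a T-score of −2.5 or below, so BMD, or FRAX calculated with BMD, would predict itself.

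**The case against.** Section 8.1.2.2 names none of FRAX, height loss or antiresorptive use. The only stated statistical use of FRAX is a descriptive summary in section 8.1.4, and height loss is not in the section 4 list. The study team has discretion, and section 8.1 announces a separate SAP that could settle the candidate list. This stands as a limit on the claim: inclusion is inferred from the all-factors wording and an open list. It does not remove the gap. Section 8.1.4 does not bar FRAX from the models. The bias and limitations sections (8.2.1 and 8.2.3) do not mention reverse causation, and the later SAP would start from the rule as written.

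A reader might infer that FRAX is built from the study films. Section 4 says radiology evidence without saying which films, so that is possible but not stated. FRAX is also not a consequence of fracture. Its problem is that fracture status may be one of its inputs.

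A reader might also want every prior fracture removed. Section 1.1 calls an initial osteoporotic fracture of any type a major risk factor for a new one, so prior non-vertebral fracture is a legitimate candidate. Antiresorptive use mixes reverse causation, confounding by indication and possible benefit, so simply dropping it is only one defensible choice.

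**Conclusion.** The gap is real and should be closed. Followed literally, the rule admits to the fracture model a predictor that can contain the outcome and others that can follow it, and it admits BMD to a model for a BMD-defined outcome.

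The documents do not support saying that consequences of fracture will be reported as risk factors, that treatment will look harmful, or that true risk factors will be displaced. Retention ranged from 44% to 100% across the assumed effects. The odds ratio for antiresorptive use ran from 0.85 to 5.0, and in some scenarios it stayed protective. Displacement of other factors was not examined. The simulation adjusted for age only and did not run the full backward elimination. The supported conclusion is that consequences or restatements of fracture can be reported as risk factors, to a degree that rests on assumed treatment shares and effect sizes.

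**What to change.** Amend section 8.1.2.2 to list the candidates for each model and add the following.

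- **Vertebral-fracture model:** exclude FRAX, height loss and prior vertebral fracture, and tabulate them by case status. FRAX components may be used singly, but the prior-fracture component must leave out vertebral fractures and anything read from study films. Otherwise the outcome returns through the component. Keep prior non-vertebral fracture as a candidate. Section 6.1.2.1 already collects anatomical site, so the split needs no new data. State how history of osteoporosis is handled, since part of it may rest on an earlier vertebral fracture.
- **Densitometric-osteoporosis model:** exclude BMD and FRAX calculated with BMD, which are circular with a T-score outcome. Also exclude history of osteoporosis, which may restate an earlier BMD diagnosis.
- **Antiresorptive use:** report it separately as subject to confounding by indication, with a sensitivity analysis with and without treated women.
- **Reporting:** describe retained variables as associated factors.

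The cost is wording only. The downside is fewer candidates and a weaker apparent model fit.

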8.3 Sample Size and Power Calculations

The sample size of the study was calculated based on prevalence data per age group several large epidemiological studies [29-32, 36]. As the prevalence of vertebral fractures increases with age, the sample size will be determined as per age group by setting a lower limit for each assumed age-based prevalence rate (Table 8.3.1), using Clopper-Pearson exact method [52] to compute the lower bound of the corresponding 95% CI at a 5% precision. A sample size of 545 at each geographic region will be statistically sufficient to cover all age groups in detecting the prevalence of vertebral fractures, assuming a 5% withdrawal rate for the spinal radiographs in the study. Considering geographic distribution (5 regions), a total sample size of approximately 2700 postmenopausal women aged 50 or above will be enrolled for the study. In addition, this sample size will yield a generally over 90% power at a 0.05 significance level to detect a geographic impact for the fracture prevalence by an odd ratio at 1.40 or 1.50, by using a univariate logistic model in estimating the change in probability.

Assuming a 40% nonresponse rate in population-based studies [56] and 5% ineligibility rate [32], invitation letters will be posted to approximately 4750 women in all regions.

Table 8.3.1 Sample Size Calculation by Age Group based Prevalence

Age group	Sample size	Assumed Prevalence	95% CI Lower Limit
50 - 54	44	5.0%	1.0%
55 - 59	81	7.0%	3.0%
60 - 64	100	12.0%	6.0%
65 - 69	90	16.0%	10.0%
70 - 74	80	20.0%	12.0%
75 - 79	70	23.0%	15.0%
>80	53	37.0%	26.0%

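### Section 8.1.2.2 screens risk factors on a crude P value, so a true vertebral fracture risk factor that is commoner in younger women can be dropped before any age adjustment

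*Combined protocol and SAP*

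**What the plan says.** Secondary objectives 2 and 3 (Section 2.2) are to identify risk factors for vertebral fracture and for densitometric osteoporosis. Section 8.1.2.2 sets out the procedure for both.

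- **Screen.** "Initially, a single logistic regression for bivariate analysis will be used to give a percentage tabulation", with an odds ratio and P value for each parameter. Then: "A P value of 0.25 or less will be the criterion [54] for an entry into a multivariate logistic model".
- **Override.** "Also, all clinically relevant variables, regardless of a probability level, will be included in the final model at the discretion of the study team". No list of such variables is given.
- **Elimination.** "A stepwise backward method to eliminate non-significant variables will be performed until all remaining variables in the model have a P value less than 0.1".
- **Age.** "In the bivariate and multivariate analysis, age, BMD, and BMI will be fitted as continuous variables". This fixes the form in which age enters. It does not put age into the screening model of every other candidate.

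Age and region are the two sampling strata (Section 3.5). On age, Section 8.3 says: "As the prevalence of vertebral fractures increases with age, the sample size will be determined as per age group".

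**The concern.** With a steep age gradient in the outcome, the crude odds ratio of any factor whose frequency changes with age mixes the factor's effect with that of age. If a harmful factor is commoner in younger women, the two pull in opposite directions and the crude odds ratio moves towards 1, or below it. The plan's own List of Definitions says that a confounder can hide a real association, and this screen leaves room for that.

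The loss is hard to recover. Backward elimination only removes variables, and the goodness-of-fit tests in Section 8.1.2.2 are not set up as a re-entry step. A masked factor that nobody forces in would leave the analysis on the strength of an unadjusted P value. Elsewhere the plan does deal with age: prevalence is age-standardized (8.1.1, 8.1.2.1), and the exploratory models allow adjustment for age and region (8.1.3).

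**Working it through.** **Inputs from the documents.** Table 8.3.1 gives 44, 81, 100, 90, 80, 70 and 53 women per region in the seven age groups, with assumed prevalences of 5, 7, 12, 16, 20, 23 and 37%. There are five regions and 5% radiograph withdrawal. The screening threshold is P ≤ 0.25. Odds ratios of 1.40 and 1.50 are the sizes Section 8.3 plans for, although for a regional effect.

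**Reproducing the plan's sample size.** The age groups sum to 518. 518 / 0.95 = 545.3, which matches the stated 545. 5 × 545 = 2,725, which matches approximately 2,700. Evaluable women: 5 × 518 = 2,590. Expected cases: 5 × Σ(n × prevalence) = 430, or 16.6%.

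**Age gradient.** 37 / 5 = 7.4-fold in prevalence. As an odds ratio: (0.37/0.63) / (0.05/0.95) = 11.2.

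**Assumptions (not in the documents).** A binary factor has exposure falling linearly from age 50 to age 90, evaluated at group midpoints 52.5 to 77.5, and at 84 for the oldest group. Its odds ratio is the same at every age, and total prevalence in each age group is held at Table 8.3.1.

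**Formulas.** Collapse over age to a 2×2 table: exposed cases A, exposed non-cases B, unexposed cases C, unexposed non-cases D. The crude log odds ratio is ln(AD/BC), its SE is √(1/A + 1/B + 1/C + 1/D), and m is their ratio. P ≤ 0.25 two-sided means |z| ≥ 1.150, so the chance of passing is Φ(m − 1.150) + Φ(−m − 1.150). For the age-adjusted screen, m is ln(OR) divided by the inverse-variance pooled SE over the seven age groups.

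**Worked case: 40% falling to 10%, true OR 1.4.**
- Expected counts: A = 121.1, B = 574.8, C = 308.8, D = 1,585.3.
- Crude OR = (121.1 × 1,585.3) / (574.8 × 308.8) = 1.08. The log is 0.079, the SE 0.118, and m = 0.67.
- Crude pass: Φ(−0.48) + Φ(−1.82) = 0.32 + 0.03 = 35%.
- Adjusted: pooled SE 0.124, m = 0.336/0.124 = 2.72, pass = Φ(1.57) = 94%.

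**Range.** Chance of passing, crude / age-adjusted:

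| Exposure, age 50 to 90 | OR 1.4 | OR 1.5 | OR 2.0 |
|---|---|---|---|
| 40% to 30% | 88% / 97% | 96% / 99% | 100% / 100% |
| 40% to 20% | 67% / 96% | 84% / 99% | 100% / 100% |
| 40% to 10% | 35% / 94% | 53% / 98% | 99% / 100% |
| 25% throughout | 94% / 95% | 98% / 99% | 100% / 100% |

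Simulated studies of the same setting agree. At OR 1.4 the crude pass rates are about 88%, 65% and 34% for the three falls. At OR 1.5 they are about 85% for 40% to 20% and 50% for 40% to 10%. For exposure unrelated to age at OR 1.4, simulation gives 92.5% crude and 93.5% adjusted. The brief and the verdict use the simulated figures.

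**Steeper falls and rare factors.** These are spread across the seven age groups rather than ages 50 to 90.
- 50% to 20%: the crude screen passes 31% at OR 1.4 and 48% at OR 1.5.
- 50% to 10%: it passes 35% at OR 1.4, 26% at OR 1.5 and 80% at OR 2.0. At OR 1.3 the crude OR is 0.87 and the factor passes 53% of the time, nearly always with the sign reversed. The multivariable model could then correct the sign if age is retained.
- 10% to 5%: at OR 1.4, adjustment raises the pass rate only from 43% to 71%.

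**The case against.** **Such factors are not usually discarded.** A reader might infer that true factors commoner in younger women are generally lost. The figures do not support that. A majority loss needs both a steep fall in exposure and a modest odds ratio. With a fall from 40% to 30%, or an odds ratio of 2.0 in most patterns, the factor is kept. No listed questionnaire variable is shown to have a steep fall, because the documents give no age distribution for any of them. This stands, and it limits the point to a conditional one.

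**The override clause.** It would also go too far to say that a screened-out factor is never age-adjusted and is bound to be reported as unassociated. Clinically relevant variables have a written route in, whatever their P value. That reduces the loss by an amount that cannot be calculated. It does not remove the loss: the choice is discretionary, has no list, and may be made after the crude results are seen. The factors least protected are those not already recognized, which are the ones an objective to identify risk factors is meant to find. The plan also does not say whether a variable brought in this way is exempt from elimination at P < 0.1.

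**Null factors.** The opposite error, a null factor that rises with age entering too easily, is not a demonstrated harm. In simulation, a null factor rising from 10% to 40% entered in 86% of studies under the crude screen. With age in the model it met P < 0.1 in about 4%, against 7% under the adjusted screen.

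**Scope.** The gradient in Table 8.3.1 is for vertebral fracture. None is given for densitometric osteoporosis, so objective 3 shares the logic but not the numbers. No calculation here supports the region term; it is a harmless adjustment for a sampling factor.

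**The separate SAP.** Section 8.1 says one will be written, and it could settle this. Nothing in the present text promises that it will.

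**Conclusion.** The concern holds in a conditional form. Section 8.1.2.2 states a crude screen, and Table 8.3.1 assumes an outcome gradient strong enough for that screen to hide a real factor. At a true odds ratio of 1.4, the crude screen passes about 88% of studies for an exposure fall of 40% to 30%, about 65% for 40% to 20%, and about 34% for 40% to 10%, against about 94-97% with age included. At 1.5 it passes about 85% for 40% to 20% and about 50% for 40% to 10%, against about 98-100%. At 2.0 these patterns are almost always kept.

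These figures rest on the assumed exposure gradients, on an odds ratio constant across age, on the Table 8.3.1 age mix and prevalences, and on the factor not being forced in. They apply to objective 2. For objective 3 the direction of the problem is the same and its size is unknown. The plan should be changed because the remedy costs almost nothing, not because a particular factor is known to be lost.

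**What to change.** In Section 8.1.2.2, and in the separate SAP:

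1. Include age (continuous) and region (categorical) in every screening regression, and apply P ≤ 0.25 to the candidate's adjusted term.
2. Keep age in the multivariable model regardless of its P value.
3. Present the crude odds ratios and percentage tabulations as description only, with no role in selection.

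This takes a few sentences and one or two extra covariates per screening model, and needs no new data. When exposure is unrelated to age, adding age leaves the chance of passing essentially unchanged (94% crude against 95% adjusted at OR 1.4).

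### Section 8.1.2.2 keeps clinically relevant variables whatever their P value but also eliminates until every P value is below 0.1, and region, a sampling stratum, is not protected from removal

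*Combined protocol and SAP*

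**What the plan says.** Section 8.1.2.2 builds the risk-factor models for vertebral fracture and for densitometric osteoporosis in stages.

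- **Entry.** Each variable is screened in a single-variable logistic regression: "A P value of 0.25 or less will be the criterion" for entering the multivariable model.
- **Forced inclusion.** Next to the entry rule: "all clinically relevant variables, regardless of a probability level, will be included in the final model at the discretion of the study team". The variables are not listed and no date is set for choosing them.
- **Elimination.** The following paragraph: "A stepwise backward method to eliminate non-significant variables will be performed until all remaining variables in the model have a P value less than 0.1". No variable is exempted.
- **Coding.** "In the bivariate and multivariate analysis, age, BMD, and BMI will be fitted as continuous variables", and "Geographic region grouping study sites will be fitted as a categorical variable". This fixes how age and region enter, not whether they stay.

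Section 3.5 gives both a design role: "The subjects will be sampled and stratified according to the following factors", namely age in seven groups and region. The regional levels are "Five (5) regions in China: North, South, Southeast, Southwest, and Central". Section 8.1 says a separate SAP will be written, but defers nothing about variable selection to it. By contrast, Section 8.1.1 says any age standardisation to regional distributions will be specified in the SAP before database lock.

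**The concern.** A clinically relevant variable with P = 0.3 must stay under the inclusion sentence and must go under the elimination sentence. The final model therefore cannot be derived from the plan. Because the forced set is discretionary and undated, it could be settled after the odds ratios are known. Risk factors for the two outcomes make up two of the three secondary objectives (Section 2.2), and Section 3.1 intends to build a fracture risk model from the analyses.

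Region is the variable most exposed. It was fixed by the sampling scheme and groups the sites. If it is dropped, any factor whose frequency differs by region, such as income, diet or calcium use, is compared across regions as well as within them, and takes up part of the regional difference in fracture risk.

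**Working it through.** **Inputs**
- Table 8.3.1: 44 + 81 + 100 + 90 + 80 + 70 + 53 = 518 women per region. Expected cases are 2.20 + 5.67 + 12.00 + 14.40 + 16.00 + 16.10 + 19.61 = 85.98, so prevalence is 85.98/518 = 16.6%.
- Section 8.3: about 2,700 women, 5% without radiographs, so 2,700 × 0.95 = 2,565 analysed, or 513 per region. Expected cases: 0.166 × 2,565 = 426.
- Section 8.3: regional odds ratio (OR) 1.40 or 1.50. The plan does not say which regions are contrasted.
- Assumed: equal regions, the Table 8.3.1 age mix in each, no clustering by site.

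**The plan's own figures.** 518/0.95 = 545.3, matching the stated 545 per region. For the stated power of generally over 90%, take two regions against three at OR 1.40. The odds are 0.166/0.834 × 1.40 = 0.2787, giving a risk of 21.8%. With 1,080 v 1,620 women the pooled standard error is about 0.0153. Then 0.0519/0.0153 − 1.96 ≈ 1.43, a power of about 92%. OR 1.50 gives 98%. One region against four gives only 77-79% at OR 1.40 and 91-92% at 1.50. The claim therefore reproduces for favourable single-degree-of-freedom contrasts. Elimination of a five-level factor uses 4 df.

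**Chance that region is removed, without covariates.** Removal means the 4-df likelihood-ratio statistic falls below 7.78, the 90th percentile of chi-square on 4 df. Its noncentrality is λ = 2 × 513 × Σ[q ln(q/q̄) + (1−q) ln((1−q)/(1−q̄))], where q is the risk in each region and q̄ the mean. At OR 1.40:
- evenly spaced, highest v lowest 1.40, centred on 16.6%: λ = 5.0, removed in 47%
- one region v four: λ = 7.3, removed in 32%
- two regions v three: λ = 10.8, removed in 16%

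The same three patterns give 78%, 73% and 64% at OR 1.20, and 32%, 16% and 5% at OR 1.50.

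**With age and a region-related factor in the model (simulation, 1,000 runs per pattern).** Adjusting for a strong predictor raises removal somewhat:

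| Regional OR | Region removed at P≥0.1 |
|---|---|
| 1.20 | 70-79% |
| 1.40 | 26-52% |
| 1.50 | 10-38% |

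The low end is two regions against three; the high end is the even spread. Repeat simulations with slightly different set-ups move these by several points. Two v three came out at 18% and 21% at OR 1.40, and at 7% at OR 1.50. With no regional effect, region is removed in about 90% of studies, as expected for a test at 0.1.

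**Consequence for a factor with no effect.** Assume exposure of 10, 20, 30, 40 and 50% across the five regions, in the same order as risk. At even-spread OR 1.40, with the lowest region at 16.6%, the risks are 16.6, 17.8, 19.1, 20.4 and 21.8%. With region omitted:
- exposed risk = Σ(e·q)/Σe = 0.2999/1.5 = 0.1999
- unexposed risk = Σ((1−e)·q)/Σ(1−e) = 0.6565/3.5 = 0.1876
- OR = (0.1999/0.8001)/(0.1876/0.8124) = 1.08

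The same sums give 1.10 for two regions v three, 1.07 if only the highest-exposure region is at higher risk, and 0.93 if only the lowest-exposure region is. With region kept, the OR is 1.00. In simulation at OR 1.40, following the elimination rule keeps this null factor at P<0.1 in about 12-15% of studies, against the nominal 10% with region always in.

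**The case against.** **The sentences may not conflict.** The inclusion sentence follows the entry rule directly and precedes the elimination paragraph. It can be read as a waiver of the 0.25 entry threshold only, or as a forced set with elimination applied to the rest. Both readings are possible. But the sentence speaks of the final model, and the text does not choose. On the entry-waiver reading, region remains open to removal.

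**The separate SAP could settle it.** It could, but Section 8.1 does not commit it to do so.

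**Region would usually survive at the design effect.** A reader might infer from the missing exemption that region would normally be eliminated. The plan's figures do not support that. At OR 1.40 removal is at most about one study in two, at 1.50 it is less, and removal becomes usual only for differences up to about 1.3. What stands is that region is unprotected.

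**Age is not realistically at risk.** Correct: its assumed prevalence runs from 5% to 37%.

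**Region is a blunt control.** Also correct. There are 8-10 sites in five regions (Section 3.2), and scanner and interviewer consistency are set by site. Fractures are read by blinded radiologists and BMD is cross-calibrated. Keeping region does not remove site effects within a region.

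**Conclusion.** The point holds as an unresolved conflict between two selection rules, with one avoidable consequence: a sampling stratum can be dropped from the risk-factor models. At the plan's own OR of 1.40 this would happen in roughly a quarter to a half of studies, at 1.50 in about 10-40%, and at 1.20 in about 70-80%. The resulting bias is small: an OR of about 1.08-1.10 for a null factor at a regional OR of 1.40, and two to five percentage points of extra false retention.

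These sizes rest on the regional pattern, equal regions and, for the bias, a 10-50% exposure gradient that has no source in the documents. The direction of the bias depends on that gradient. The calculations cover the fracture model only; the same wording governs the osteoporosis model.

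A reader might also infer that discretionary retention makes the reported intervals invalid. That goes too far. Keeping variables regardless of P value does no such damage by itself. Selecting on P values does weaken nominal coverage, but that comes with any backward elimination and would remain after the change below. The change is worth making because it is nearly free.

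**What to change.** Reword Section 8.1.2.2, for both outcomes, to state that:

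1. age (continuous) and region (categorical) are in every multivariable model and exempt from elimination;
2. any other clinical variables to be forced in are named in the SAP before database lock;
3. backward elimination at P<0.1 applies only to the remaining candidates.

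Delete the clause leaving the choice to the study team's discretion.

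The cost is wording plus five degrees of freedom (one for age, four for region) against about 426 expected fracture cases. No data collection changes.
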